## **7.0 RISKS - STUDY DRUG**

---

**7.1 Risks:** Side effects of LEV exposure have been well characterized in clinical trials using LEV dose ranges of 1000-3000 mg/day. The most common symptoms are neurological, including somnolence (15% of patients), asthenia (15%), headache (14%), dizziness (13%), and ataxia (3%) (Ben-Menachem and Falter, 2000; Cereghino et al., 2000; Shorvon et al., 2000). Patients also reported a slightly higher incidence of infection (13% of patients). Up to 13% of patients also experienced adverse neuropsychiatric symptoms. In most of these patients, the symptoms have been mild, including agitation, hostility, apathy, anxiety, emotional lability, and depression (Gambardella et al., 2008). About 1% of patients have experienced serious neuropsychiatric symptoms including hallucinations, suicidal ideations, or psychosis (Kossoff et al., 2001; Mula et al., 2003). In these reports, symptoms occurred mostly within the first month of therapy. Dose reduction or discontinuation has led to resolution of symptoms in cases reported. Conversely, LEV has no major adverse effects on cognitive function (Neyens et al., 1995), which is an improvement over more traditional anti-epileptic agents (Dooley and Plosker, 2000). Presently, there are no sufficient data to recommend treatment with LEV during pregnancy. Case reports have indicated Stevens-Johnson Syndrome (SJS) is an exceedingly rare side effect of LEV administration (Zou et al., 2012). In a meta-analysis of 26 double-blind, randomized, placebo-controlled trials (2832 patients), no dose-response relationship was found for any side effects (Verrotti et al., 2015).

**7.2 Absorption and Distribution:** LEV is rapidly and almost completely (>95%) absorbed (Rossetti and Bromfield, 2005) after oral administration of doses ranging from 250 to 5000 mg, with peak serum concentrations occurring approximately 1 hour after dose and steady state concentrations are reached within 48 hours (Gambardella et al., 2008). The oral bioavailability of LEV tablets is 100%. Food does not affect the absorption of LEV. The volume of distribution is 0.5-0.7 L/kg (Patsalos, 2004). LEV does not bind to plasma proteins and has linear pharmacokinetics that are time-invariant with low intra- and inter-subject variability (Patsalos, 2004, 2000).

**7.3 Metabolism and Elimination:** LEV is not extensively metabolized in humans. The major metabolic pathway is the enzymatic hydrolysis of the acetamide group by a plasma hydroxylase. This produces the inactive compound carboxylic acid metabolite ucb L057 (24% of dose). LEV does not undergo hepatic metabolism (Nicolas et al., 1999). The serum half-life is 6 to 8 hours (Krasowski, 2010). LEV is eliminated from systemic circulation by renal excretion as unchanged drug (66% of the dose). Total body clearance is 0.96 mL/min/kg and renal clearance is 0.6 mL/min/kg. The metabolite ucb L057 is renally excreted with a renal clearance of 4 mL/min/kg. Clearance is rapid, so that within 48 hours approximately 93% of an oral dose is eliminated. In patients with renal impairment, doses should be reduced in accordance with creatinine clearance (Patsalos, 2004).

**7.4 Interactions with other Drugs:** Reviews have indicated that LEV does not affect the metabolism of other drugs, including antipsychotics (Besag and Berry, 2006).

## **7.5 Minimizing Risk for Study Drug:**

**7.5.a Dosage:** As mentioned above, clinical indications for LEV use in epilepsy range from 1000-3000 mg/day. Our study will be using 250 mg BID. As reviewed in both section **3.0** and **6.6.b**, human functional MRI studies have demonstrated that low doses decrease hippocampal activity and improve memory task performance in patient cohorts outside the FDA-approved indications for LEV.

**7.5.b Screening Process:** The screening visit will include a Screening Form that has a LEV Screening section. It will assess neuropsychological history to address the neuropsychological side effects and assess history of rashes in response to medications to address the possibility of a SJS reaction. Additionally, a blood draw to obtain a CBC and BMP will assess creatinine levels, to address renal function, and white blood count, to address possibility of infection, in each patient at each visit. Blood draws for a CBC and BMP will not occur if there is a record of recent CBC or BMP values (within past 45 days). Lastly, females will perform a pregnancy test at each visit to ensure no teratogenic effects.

**7.5.c Usage as add-on therapy for psychosis cohort:** LEV has no known major drug interactions. Therefore, the psychosis cohort will use LEV as an add-on therapy with the antipsychotic medications.

**7.5.d Driving after drug administration:** Because somnolence is a major side effect of LEV, we require that participants who drive themselves to Vanderbilt Psychiatric Hospital on Day 1 (first day of drug administration) will take a Standardized Field Sobriety Test to ensure they are safe to drive themselves home. This test is based on available data provided by the National Highway Traffic Safety Administration. It will be administered before initial drug administration and as the final assessment on Day 1 immediately before the participant leaves. It takes about 5 minutes to complete. If the participant scores above an impairment threshold on any portion of the test, we will purchase a car service (Uber/Lyft) to drive the participant home and back to Vanderbilt Psychiatric Hospital on another day to obtain their vehicle.

**7.6 Risk/Benefit Ratio:** When the safety record outlined above is considered, the risks of participation in this study are low. Long-term safety of LEV appears to be very favorable. Subjects participating in these studies will receive MRI assessment and basic drug and pregnancy screening (when applicable) at no cost to them. Otherwise, there are no direct benefits to the subjects participating in this research. The long-term potential benefit of this study is a mechanistically directed approach toward identifying a reliable biomarker for psychotic disorders. Every research study requires the potential benefits to outweigh the potential risks of the study. The potential benefit of establishing a biomarker is significant for public health, including for patients, their families, communities, and healthcare systems. While the study procedure confers greater than minimal risk, the low likelihood of serious adverse effects is outweighed by the potential public health benefits stemming from the potential results of this study and subsequent studies based on these results.

With respect to MRI scanning, the MR system requires the use of rapidly varying magnetic gradient fields and strong radio frequency fields. These switched gradient and radio frequency fields conform to the guidelines established by the US FDA for time varying magnetic fields in MR devices. No serious or lasting incidents or side effects associated with the use of high field magnets have been reported. Based on this experience, and valid scientific evidence, the FDA has found that this does not pose a significant risk to human subjects.

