### **Inclusion criteria for psychosis subjects**

1. Men and women age 18 - 65.
2. Communicative in English.
3. Provide voluntary, written informed consent.
4. Physically healthy by medical history.
5. BMI > 17.5 and < 45.
6. Diagnosis of a psychotic disorder confirmed by Structured Clinical Interview for DSM-V (SCID) or diagnostic interview with a trained clinician.
7. Stable medication regimen over at least the past two weeks, including the use of either an oral or intramuscular administration of an antipsychotic medication.
8. For females, no longer of child-bearing potential, or agreeing to practice effective contraception during the study (e.g., established use of oral, injected or implanted hormonal methods of contraception; placement of an intrauterine device [IUD] or intrauterine system [IUS]; barrier methods: condom with spermicidal foam/gel/film/cream/suppository or occlusive cap [diaphragm or cervical/vault caps] with spermicidal foam/gel/film/cream/suppository; male partner sterilization; or true abstinence when this is in line with the preferred and usual lifestyle of the subject); and,
9. For females of child-bearing potential, must have negative urine pregnancy test at time of screening visit and before each testing day.
10. Not breastfeeding/nursing at time of screening or at any time during the study.

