## **6.0 STUDY PROCEDURES**

---

**Overview:** There are nine components of the study:

1. Screening and Consent
2. Diagnostic Interview
3. Clinical Assessment (psychosis patients only)
4. Neurocognitive Assessment
5. MRI Scanning
6. Drug Administration
7. Blood draws
8. Urine pregnancy test
9. Mid-intervention phone call

Each component will be described in detail below. The entire study will be completed in about two weeks. The number of study visits depends on whether the planned study procedures can be completed in the specified time period and the availability of both the participant and necessary resources (i.e. availability of the MRI scanner). The specific rating scales completed will be dependent upon diagnosis and the time since an individual participated in the PGPR study, as many of the measures overlap and assess symptomatology based on specific time-intervals (i.e., the last 2 weeks).

**6.1 Screening and Consent:** Subjects will be asked if they would like to participate in the current study. This screening will occur over the phone or in person using the Screening Form. Informed consent will be obtained by study personnel directly involved in the research (i.e. research staff or graduate student). Personnel have completed IRB training and have considerable experience running studies on psychiatric populations.

Informed consent will be obtained in the research offices at the Psychiatric Neuroimaging Program. A research staff member will explain the applicable procedures and the possible risks and benefits to the subjects. The details of the informed consent procedure are as follows:

1. The investigator or research staff and the subject will read together the entire consent form
2. The subject will be asked details about the study. To document that the subject has read the consent form and has the capacity to understand the most important details, the investigator will use the appropriate Informed Consent Survey. The questions will be read by the investigator or research staff and the answers will be recorded (appropriate response listed in *Italics* in the Informed Consent Survey). If the subject is unable to answer any of the questions, or if the subject demonstrates a lack of understanding, the investigator or research staff member will then review the details of the study again. Subjects who are unable to answer the questions, even after additional information is provided, will be excluded from the study.

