**6.5 MRI Procedures:** MRI scans of the brain will be obtained using the MRI scanners in the Center for Human Studies in the Vanderbilt University Institute for Imaging Science (VUIIS), located in the Vanderbilt Hospital and Medical Center North. This will require approximately 60-90 minutes. There will be a total of three MRI scans in this study (baseline assessment, two hours after the initial LEV dose, and after two-week intervention of LEV).

**6.5.a MRI Screening:** The participant will fill out the MRI Procedure Screening Form. The purpose of this form is to ensure that there are no implanted medical devices or metals that could injure the subject if exposed to a high magnetic field. This form will be filled out in a private room adjacent to the MRI scanner and reviewed by the MR Technologist and the research assistant.

**6.5.b Scanning Procedures:** Imaging studies will take place on a Phillips 3.0 T MRI scanner. The magnet and the magnet's control console are in separate rooms, but the investigator and the subject will be in voice communication at all times, and the investigator will be able to see the subject through a window. All data acquired on the scanner will be securely transferred over the Vanderbilt network to the Institute of Imaging Science's server. Imaging data will be de-identified and only be accessible to the PI, co-investigators, and VUIIS personnel. Scanning procedures may include: 1) Structural imaging, 2) Resting state functional imaging, 3) ASL imaging to non-invasively measure cerebral blood flow, and 4) Functional imaging with task – while in the scanner, participants will view images that include faces,

objects and scenes. Images are projected to a mirror above the participants head from a projector located outside the scanner room. Some runs will repeat the same face or object, some runs will present different images. Participants will complete between 1-8 runs of this task. To maximize participant's attention to the images, participants will be instructed to push a button to detect targets. Targets may include image repeats or changes in the image (e.g., image size). This task is similar to the reported in McHugo et al., 2019.

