**6.6.b. Timing Rationale:** We selected a two-hour duration for the first imaging assessment based on LEV's absorption and clearance data. The pharmacokinetics will be reviewed in more detail in sections 7.2 and 7.3. Briefly, LEV is rapidly and almost completely absorbed after oral administration, with peak serum concentrations occurring approximately one hour after dose (Gambardella et al., 2008). Based on a study that measured LEV plasma concentrations ( $\mu\text{mol/L}$ ) over time after oral ingestion of varying doses of LEV (500-5000mg) in healthy volunteers, LEV levels will be approximately 9.75 mcg/mL (57.3  $\mu\text{mol/L}$ ) at two hours (Patsalos, 2004). Therefore, two hours after LEV administration is the earliest time-point where we can assess study participants at a sub-therapeutic epilepsy dose (10-40 mcg/mL) of LEV (Bakker et al., 2015, 2012; Lyseng-Williamson, 2011).

**6.6.c Duration Rationale:** We selected a 2-week duration because of other studies that have been able to safely demonstrate changes in cognitive performance and changes in hippocampal activation (Bakker et al., 2015, 2012) after 2 weeks of LEV intervention in patient cohorts outside the FDA-approved indications for LEV.

**6.6.d Compliance:** We will assess compliance using the Medication Adherence Questionnaire, a medication count after two weeks, and a test for LEV blood levels.

**6.6.e Concomitant medications:** We will allow concomitant use of any medication approved by the US FDA unless specified in our inclusion/exclusion criteria (e.g. normal controls using psychotropic medications). Reviews have indicated that LEV does not affect the metabolism of other drugs, including antipsychotics (Besag and Berry, 2006).

**6.7 Blood Draw:** Subjects will undergo three separate blood draws. The first blood draw will occur during the

Screening and Enrollment visit. The second blood draw will occur during the short-term intervention assessment. The third blood draw will occur during the long-term intervention assessment. Both visits will use blood draws to assess GFR and CBC, as addressed in the study drug risks below. During the short-term intervention visit, we will check LEV levels for the study of a dose-response relationship with blood flow. During the long-term intervention visit, participants will undergo a blood draw to check LEV levels to ensure compliance with taking the study medication.

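### The 45-day laboratory waiver in 7.5.b is not limited to screening or to the same test; followed literally, it cancels the two-week CBC/BMP and can leave no creatinine result

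*Combined protocol and SAP*

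**What the plan says.** Section 7.5.b (Screening Process) lists laboratory tests as one of the measures that reduce study-drug risk. The BMP supplies creatinine for renal function. The CBC supplies "white blood count, to address possibility of infection, in each patient at each visit". The next sentence is the exception: CBC and BMP draws "will not occur if there is a record of recent CBC or BMP values (within past 45 days". It is worded as a rule, not as an option for staff.

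Section 6.7 (Blood Draw) lists three draws, at screening, the short-term visit and the long-term visit. It then states: "Both visits will use blood draws to assess GFR and CBC, as addressed in the study drug risks below". That clause sends the reader to section 7, where the waiver sits. Section 6.7 also plans blood at the long-term visit for another purpose: "participants will undergo a blood draw to check LEV levels to ensure compliance with taking the study medication".

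On timing, the section 6.0 overview says: "The entire study will be completed in about two weeks". Section 6.6 gives two weeks of 250 mg twice daily after a first dose of 500 mg. Section 6.5 places the short-term scan "two hours after the initial LEV dose".

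On renal function, 7.3 says: "In patients with renal impairment, doses should be reduced in accordance with creatinine clearance". Among the eligibility criteria in 4.0, inclusion 4 reads "Physically healthy by medical history", and exclusion 11 bars conditions that preclude the study drug, as defined in a Screening Form that is not part of the documents.

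**The concern.** The exception is wider than the safeguard can bear, in two ways.

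**Timing.** The window is 45 days and the treatment period is 14. Nothing stops the study's own screening panel from counting as the recent record. A participant on schedule who is tested at screening would then have no further CBC or BMP, although the preceding sentence asks for them at each visit. The two-week panel is the one that matters: a panel taken about two hours after the first dose says little about the effect of the drug.

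**Test.** The waiver joins the two tests with *or*. Read literally, a recent CBC is enough to skip the BMP, so someone could be dosed with no creatinine on file in a plan that itself links dose to creatinine clearance.

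What is at stake is whether the study obtains any haematology or renal result after sustained dosing. Such a result would come too late to change that participant's dose. It would prompt follow-up of the participant and inform the six-monthly adverse event review in 9.0.

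**Working it through.** The plan gives no derived figure to reproduce here. The check is date arithmetic, a table for the *or*, and a rough sizing of the renal issue.

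**Inputs.** Waiver window 45 days (7.5.b). Treatment 14 days (6.6). Panels nominally due at screening, the short-term visit (Day 1) and the two-week visit (7.5.b, 6.7). Up to 60 participants (5.3). The gap *s* from screening to Day 1 is not stated; I take 0 to 7 days as typical and also find the limit.

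**1. Tested at screening.** Age of the result at two weeks = *s* + 14.

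- *s* = 0: 14 days, waived.
- *s* = 7: 21 days, waived.
- *s* = 31: 45 days, still waived.
- *s* = 32: 46 days, so the draw returns.

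Section 13.0 expects contact with subjects to be completed within one month. Taking that as 30 days, *s* is at most 30 − 14 = 16, well inside the limit.

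**2. Admitted on an outside record.** Let *a* be the age of the record at screening, from 0 to 45 whole days (46 values).

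- If *a* + *s* ≤ 31, the record is at most 45 days old at two weeks and waives that panel.
- If *a* + *s* is 32 to 45, it is still valid on Day 1 but has expired by two weeks, so the panel is drawn.
- If *a* + *s* > 45, it has expired by Day 1. The Day 1 panel is drawn, is 14 days old at two weeks, and waives the two-week panel.

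The two-week panel is therefore drawn only for the 14 values *a* = 32 − *s* to 45 − *s*. For any *s* from 0 to 31 all 14 lie within 0 to 45, so the panel is lost for 46 − 14 = 32 values, and 32/46 = 70%.

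| Gap *s* | Waived by outside record | Drawn at two weeks | Waived by new Day 1 panel | Lost |
|---|---|---|---|---|
| 0 | *a* 0–31 (32) | *a* 32–45 (14) | none | 32/46 |
| 7 | *a* 0–24 (25) | *a* 25–38 (14) | *a* 39–45 (7) | 32/46 |

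If all 60 entered this way with an even spread of ages, 60 × 32/46 = 41.7, so about 42 two-week panels would be lost and 18 kept. If all 60 were tested at screening, all 60 would be lost.

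**3. The *or*.**

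| Recent record | Literal reading | Same-test reading |
|---|---|---|
| Neither | draw both | draw both |
| BMP only | draw neither; no white count | draw CBC |
| CBC only | draw neither; no creatinine | draw BMP |
| Both | draw neither | draw neither |

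**4. Size of the renal issue.** Section 7.3 gives total clearance 0.96 and renal clearance 0.60 mL/min/kg, which leaves 0.36 non-renal. Assume the non-renal part is unchanged and kinetics are linear, as 7.2 states. The study dose is 2 × 250 = 500 mg/day.

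- Renal clearance halved: total 0.36 + 0.30 = 0.66. Exposure × 0.96/0.66 = 1.45, equivalent to 727 mg/day with normal kidneys.
- Renal clearance at a quarter: total 0.36 + 0.15 = 0.51. Exposure × 0.96/0.51 = 1.88, equivalent to 941 mg/day.
- Equivalence to 1,000 mg/day, the bottom of the clinical range in 7.5.a, needs total clearance of 0.48. Renal clearance is then 0.12, and 0.12/0.60 = 20% of normal.

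**The case against.** The strongest reply is that the authors meant something narrower. The paragraph is headed Screening Process, the sentence before the waiver asks for tests at each visit, and 6.7 plans GFR and CBC at both visits. A waiver that emptied those statements would be odd, and *CBC or BMP values* can be read as each test standing in for itself. This is plausible and it stands as a reading. It does not settle the matter: the waiver directly follows the each-visit requirement, carries no limit of its own, and 6.7 defers to it. Staff could follow the text in good faith and skip the panel.

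Three stronger conclusions are tempting, and the documents do not support them.

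- A reader might infer that, for healthy controls, the two-week panel is the only objective safety measure on drug. It is not. Section 6.7 measures LEV levels at both on-drug visits, 7.5.d gives participants who drive a sobriety test on Day 1, and 6.8 requires a two-week pregnancy test of all females. The neurotoxicity scale in 6.3.f falls under a patients-only heading, but 6.6.d uses the adherence measures of the same subsection without that limit, so the scale may reach controls too.
- A reader might infer that participants will be dosed with no renal check at all. Exclusion 11 and the LEV section of the Screening Form might supply one. The form cannot be seen, so this stays open. The criterion on physical health by history lowers renal risk but measures nothing. How often someone would arrive with a CBC and no BMP is also unknown.
- A reader might infer a serious overdosing hazard. The clearance arithmetic does not show one, and 7.1 cites a meta-analysis that found no dose-response for side effects.

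**Conclusion.** The concern holds as a fault in the wording of a stated rule. As written, the waiver defeats the safeguard it qualifies: for anyone tested at screening with Day 1 no more than 31 days later, the two-week CBC and BMP are cancelled. For those admitted on outside records the loss is 70% at any gap from 0 to 31 days. That figure rests on an even spread of record ages over 0 to 45 days and on a Day 1 panel being drawn whenever the record has expired. Taken literally, the *or* also permits dosing without a creatinine result under 7.5.b, unless the Screening Form prevents it.

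The consequence is modest. Without the two-week panel there is no haematology or renal check after sustained dosing, but LEV levels, the mid-intervention phone call (6.9) and adverse event review (9.0) remain. The primary imaging comparison is untouched. This is a cheap improvement to safety monitoring; it does not show that the authors intended to omit on-drug laboratory tests.

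**What to change.** Replace the waiver sentence in 7.5.b with:

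> At screening only, the CBC and the BMP may each be replaced by a result of that same test from the past 45 days; a creatinine result must be on record before the first dose. The CBC and BMP at the two-week visit are always drawn, using the blood draw already planned for LEV levels.

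Then bring the each-visit phrase in 7.5.b and the both-visits phrase in 6.7 into line with it. The short-term panel may be kept or dropped; the text should say which.

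The cost is at most 60 extra CBC and BMP assays at two weeks, with no extra venepuncture at that visit, plus a BMP for anyone who arrives with only a CBC. If the authors already intended a screening-only, same-test waiver, the change simply records it.
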